5.5.1.5 Visit 6 (Day 15)

Please refer to Table 2 for the clinical and laboratory parameters to be collected during these visits. For study drug administration schedule, see Section5.4.5.

Effort should be made to adhere to the schedule of assessment. However, a visit window of ± 1 day will be allowed for Visit 6 (Day 15).

During the treatment period (Days 1 to 15), clinical and laboratory assessments and procedures should preferably be performed before IMP administration

The primary endpoint will be evaluated at Visit 6 (Day 15).

5.5.1.6 Visit 7 (Day 28)

An early follow-up visit will be performed at Day 28.

Version 7.0 Final Protocol, Date 24 Jun 2020

Please refer to Table 2 Schedule of EventsTable 2 for the clinical and laboratory parameters to be collected during this visit. If the patient is discharged from the hospital before this visit, efforts should be made to adhere to the visit window of ± 3 days.

5.5.1.7 Visits 8 and 9, Follow-up (Weeks 6 and 10)

These visits can be conducted either as a follow-up telephone call or in-person visit, if the patient is still hospitalized. Please refer to Table 2 for the clinical parameters to be collected during the visits.

A window of ± 5 days will be allowed for Visits 8 and 9.

5.5.2 Patient information and physical examination

5.5.2.1 Demographics

The patient's date of birth, gender, race and ethnicity will be collected at screening, and recorded in the CRF.

5.5.2.2 Medical and surgical history

Details of the patient's relevant medical and surgical history as judged by the Investigator will be collected at screening, and recorded in the CRF.

5.5.2.3 Prior medication

Details of the patient's relevant prior medication as judged by the Investigator will be collected at screening, and recorded in the CRF.

5.5.2.4 Physical examination

A general physical examination will be performed at screening and recorded in the CRF. The assessment will be reported as "normal" or "abnormal". Any abnormalities should be specified and recorded as medical history.

Body weight and height will be recorded as a part of the physical examination.

5.5.2.5 Symptom onset information

Date of symptom onset will be collected at screening, and recorded in the CRF. This data is collected to explore the time between symptom onset and start of treatment.

5.5.3 Efficacy assessments

5.5.3.1 Pulmonary function (primary efficacy assessment)

The date and time of the requirement for invasive mechanical ventilation and extracorporeal membrane oxygenation (ECMO) will be assessed at Visits 1 to 7, and recorded in the CRF.

Version 7.0 Final Protocol, Date 24 Jun 2020

5.5.3.2 MEWS score

Modified early warning system score (MEWS) will be assessed at Visit 1 (Day 1), Visit 6 (Day 15) and Visit 7 (Day 28) and recorded in the CRF.

5.5.3.3 SpO₂, PaO₂ and FiO₂

Resting peripheral capillary oxygen saturation (SpO_2) will be measured 3 times per day at Visits 1 to 7, and recorded in the CRF. For Visit 7, if the patient is discharged from the hospital prior to this visit, the SpO₂ will be performed only once at this visit.

The partial pressure of oxygen (PaO_2) and the fraction of inspired oxygen (FiO_2) will be measured at screening, at Visit 6 and Visit 7, and recorded in the CRF.

5.5.3.4 Hemogasanalysis

Hemogasanalysis will be assessed at Visits 1 to 7, and recorded in the CRF.

Analysis may for example include pH, carbon dioxide tension (pCO₂), oxygen tension (pO₂), electrolytes, lactate and hemoglobin.

5.5.3.5 Oxygen supplementation

Oxygen supplementation will be assessed at Visits 1 to 7. The date, time and amount of supplementation will be recorded in the CRF.

5.5.3.6 High-resolution computed tomography

A high-resolution computed tomography scan (HR-CT) of the chest or a chest X-ray will be performed at screening, Visit 6 (Day 15) and Visit 7 (Day 28). The HR-CT scan or the X-ray of the chest will be recorded in the CRF and reported as "normal" or "abnormal".

Any abnormalities reported at screening should be specified and recorded as medical history.

5.5.3.7 Laboratory assessments

Blood samples for determination of the laboratory assessments described in Table 3 will be drawn at screening, and at Visits 1 to 7. The date and time of blood sampling will be recorded in the CRF.

Biochemistry	Hematology
Aspartate aminotransferase (AST)	Hemoglobin
Alanine aminotransferase (ALT)	Platelet count
Total bilirubin (if >upper limit of normal also	White blood cells
conjugated and non-conjugated bilirubin)	RBC
Prothrombin Time/International Normalized Ratio (PT-INR)	Differential blood count
Fibrinogen	Hyperinflammatory parameters
Complement C3/C4	Ferritin
Cardiac troponin	LDH
Creatinine	D-dimers
C-reactive protein (CRP)	
Electrolytes (Sodium, Potassium, Calcium)	Additional testing at screening
Glucose	TB screening
	PCR SARS-CoV-2

Table 3 Laboratory assessments

All laboratory samples will be analysed at the respective local hospital laboratory according to their standard routines.

The laboratory results will be entered by the respective hospital into the study eCRF.

5.5.3.7.1 Additional testing at screening

Patients randomized to study with no clinical suspicion of active or latent tuberculosis as per study exclusion criteria (see 5.3.2) may on rare occasions test positive for TB based on lab screening. Should such situation occur, the principal investigator will decide based on the assessed benefit/risk for the patient whether or not it is in the best interest of the patient to continue in the study.

For study sites where PCR is not part of hospital routine for confirming SARS-CoV-2 diagnosis/eligibility as per study inclusion criteria (see 5.3.1), PCR test results are accepted post randomization not to delay treatment. The test can be done in specimens of different origins as decided by principal investigator. Should an enrolled patient show a negative PCR test result for SARS-CoV-2, the principal investigator will decide based on the assessed benefit/risk for the patient whether or not it is in the best interest of the patient to continue in the study. Such patient is to be excluded from the study efficacy analysis but included in the safety analysis.

5.5.3.8 Survival and hospital discharge

Data on survival and hospital discharge will be collected at Visits 7 (Day 28), Visit 8 and 9 (Weeks 6 and 10) and recorded in the CRF.

5.5.4 Safety assessments

5.5.4.1 Adverse events

5.5.4.1.1 Definitions

Adverse event (AE)

An AE is any adverse change, i.e., any unfavorable and unintended sign, including an abnormal laboratory finding, symptom, or disease that occurs in a patient during the course of the study, whether or not considered by the investigator as related to study treatment.

A treatment-emergent AE is any AE temporally associated with the use of study treatment whether or not considered by the investigator as related to study treatment.

Adverse events include:

- Exacerbation of a pre-existing disease.
- Increase in frequency or intensity of a pre-existing episodic disease or medical condition.
- Disease or medical condition detected or diagnosed during the course of the study even though it may have been present prior to the start of the study.
- Continuous persistent disease or symptoms present at study start that worsen following the start of the study (i.e., signing of informed consent).
- Abnormal assessments, e.g., change on physical examination, ECG findings, if they represent a clinically significant finding that was not present at study start or worsened during the course of the study.
- Laboratory test abnormalities are considered as AEs if they represent a clinically significant finding, symptomatic or not, which was not present at study start or worsened during the course of the study or led to dose reduction, interruption or permanent discontinuation of study treatment. An AE is any untoward medical occurrence in a patient administered a pharmaceutical product; the event does not necessarily have a causal relationship with the treatment or usage.

5.5.4.1.2 Intensity of adverse events

The intensity of clinical AEs is graded on a three-point scale – mild, moderate, severe – and is reported on specific AE pages of the CRF.

If the intensity of an AE worsens during study treatment administration, only the worst intensity should be reported on the AE page. If the AE lessens in intensity, no change in the severity is required.

If the intensity of an AE with an onset date between informed consent signature and start of study treatment and which is ongoing at the start of treatment worsens after the start of study treatment, a new AE page must be completed. The onset date of this new AE corresponds to the date of worsening in intensity.

The three categories of intensity are defined as follows:

Version 7.0 Final Protocol, Date 24 Jun 2020

□ Mild

The event may be noticeable to the patient. It does not influence daily activities, and usually does not require intervention.

□ Moderate

The event may make the patient uncomfortable. Performance of daily activities may be influenced, and intervention may be needed.

Severe

The event may cause noticeable discomfort, and usually interferes with daily activities. The patient may not be able to continue in the study, and treatment or intervention is usually needed.

A mild, moderate, or severe AE may or may not be serious, see Section 5.5.4.2. These terms are used to describe the intensity of a specific event. Medical judgment should be used on a case-by-case basis.

Seriousness, rather than severity assessment, determines the regulatory reporting obligations.

5.5.4.1.3 Relationship to study treatment

Each AE must be assessed by the investigator as to whether or not there is a reasonable possibility of causal relationship to the study treatment, and reported as either related or unrelated. The determination of the likelihood that the study treatment caused the AE will be provided by an investigator who is a qualified physician.

5.5.4.2 Serious adverse events

5.5.4.2.1 Definitions of serious adverse events

An SAE is defined by the International Conference on Harmonisation (ICH) guidelines as any AE fulfilling at least one of the following criteria:

- Fatal.
- Life-threatening: refers to an event in which the patient was at risk of death at the time of the event. It does not refer to an event that hypothetically might have caused death had it been more severe.
- Requiring inpatient hospitalization, or prolongation of existing hospitalization.
- Resulting in persistent or significant disability or incapacity.
- Congenital anomaly or birth defect.
- Medically significant: refers to important medical events that may not immediately result in death, be life-threatening, or require hospitalization but may be considered to be SAEs when, based upon appropriate medical judgment, they may jeopardize the patient, and may require medical or surgical intervention to prevent one of the outcomes listed in the definitions above.

The following reasons for hospitalization are exempted from being reported:

• Hospitalization for cosmetic elective surgery, or social and/or convenience reasons.

• Hospitalization for pre-planned (i.e., planned prior to signing informed consent) surgery or standard monitoring of a pre-existing disease or medical condition that did not worsen, e.g., hospitalization for coronary angiography in a patient with stable angina pectoris.

However, complications that occur during hospitalization are AEs or SAEs (for example if a complication prolongs hospitalization).

5.5.4.3 Reporting requirement of adverse events

5.5.4.3.1 Reporting of adverse events

Irrespective of seriousness, the following adverse events are considered as adverse events of special interest and must be reported on AE page of the CRF.

In all patients:

• AEs leading to discontinuation of study treatment

Infusion related reactions including anaphylactic/anaphylactoid reactions. In patients treated with emapalumab, the following AEs will be considered of special interest:

• All new infections.

In patients treated with anakinra, the following AEs will be considered of special interest:

• Severe neutropenia defined as neutrophil count $< 0.5 \times 10^{9}$ /l.

No other AEs are required to be reported on the AE page of the CRF

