2.2 Ethical conduct of the study

This study will be conducted in compliance with this protocol, the ICH GCP [1], applicable regulatory requirements, and in accordance with the ethical principles that have their origin in the Declaration of Helsinki) [2].

It should be noted that due to the urgency of the situation the Sponsor has for this protocol requested and been granted certain exemptions in connection to the approval in Italy to what is required for a Clinical Trial Application, certain ICH GCP requirements and when conducting a clinical trial (see Appendix 3). A study exemption to AE reporting is included in the study protocol in order to minimize clinical burden during the SARS-CoV-2 pandemic, limiting reporting to SAEs, AEs leading to premature discontinuation of study treatment, and AEs of special interest as described in the protocol (Section 5.5.4.3.1).

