5.5.4.3.2 Reporting of serious adverse events

All SAEs occurring after study drug initiation and up to the end of study visit (Visit 9, Week 10) must be reported on AE pages in the CRF and on an SAE form, regardless of the investigator-attributed causal relationship with study treatment.

Abnormal laboratory findings

Abnormal laboratory findings, if serious, must be reported on specific AE pages of the CRF.

Following laboratory variables are collected for the assessment of efficacy (see Section 6.5.3.2) at screening and during the treatment period, and are not required to be reported as SAEs as described above: WBC including differential counts, RBC, Hgb, platelet count, fibrinogen, complement C3/C4, PT-INR, and cardiac troponin; ALT, AST, total bilirubin, creatinine, ferritin, LDH, D-dimer, CRP, electrolytes (sodium, potassium, calcium), and glucose.

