### 13.1 Adverse events

All AEs will be coded using MedDRA version 21.1.

A treatment-emergent AE (TEAE) is defined as an AE with a start date/time after randomization.

The number and percentage of patients with at least one TEAE, at least one serious TEAE, including death, at least one non-serious TEAE, any related TEAE, any fatal TEAE, any TEAE leading to study treatment withdrawn and any TEAE leading to study withdrawal will be summarized.

The number and percentage of patients with at least one TEAE will be summarized in frequency tables by treatment, system organ class and preferred term. Separate tables will present TEAEs classified by relationship to study treatment or to standard of care and TEAEs classified by maximum severity. These tables will be presented by PT in descending order of frequency across all groups. Percentages will be based on the number of patients in the All Treated population for the specific treatment group.

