#### 13.1.3 Adverse events of special interest

The number and percentage of patients with treatment emergent adverse events of special interest will be presented:

- Emapalumab treatment group: Infections caused by pathogens potentially favored by IFN- $\gamma$  neutralizations such as mycobacteria, salmonella, shigella, herpes zoster and histoplasma capsulatum, and severe infusion-related reactions.
- Anakinra treatment group: Severe neutropenia.

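### Non-serious new infections are required only on emapalumab, but AEs are tabulated by arm as if collection were equal, so an apparent excess is expected at equal true rates

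*Protocol*

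**What the plan says.** Adverse event collection is deliberately restricted. Protocol Section 2.2 describes an exemption "limiting reporting to SAEs, AEs leading to premature discontinuation of study treatment, and AEs of special interest". Section 5.5.4.3.1 lists what must go on the AE page whatever its seriousness. In all patients this is infusion-related reactions and "AEs leading to discontinuation of study treatment". Two arm-specific items follow:

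- "In patients treated with emapalumab, the following AEs will be considered of special interest": the item listed is every new infection.
- "In patients treated with anakinra, the following AEs will be considered of special interest": the item listed is severe neutropenia, below 0.5 x 10^9/L.

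The section closes with "No other AEs are required to be reported on the AE page of the CRF". Serious events are handled in Section 5.5.4.3.2; they "must be reported on AE pages in the CRF and on an SAE form, regardless of the investigator-attributed causal relationship with study treatment". Section 5.5.4.13 asks for infection monitoring and pathogen data under its emapalumab heading only.

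The analysis text does not follow these differences. Protocol Section 7.3.4.1 tabulates AEs by treatment, system organ class, preferred term and severity, with separate serious and non-serious tables. Under SAP Section 13.1, patients with at least one TEAE "will be summarized in frequency tables by treatment, system organ class and preferred term", and patients with at least one non-serious TEAE are counted. Percentages are based on each arm's treated patients. SAP Section 13.1.3 summarises events of special interest by arm: selected pathogens and severe infusion reactions for emapalumab, and for the other drug "Anakinra treatment group: Severe neutropenia".

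**The concern.** A side-by-side table invites the reader to compare columns. Here the infection rows count different things: all infections on emapalumab, mostly serious ones on anakinra, and only serious ones on standard of care. A difference between columns then mixes the drug effect with the reporting rule.

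New infection is the safety item the protocol singles out for emapalumab. Protocol Section 7.1 allows the results to support regulatory approval, and SAP Section 13 allows tabulations to be supplied to the Safety Review Committee. The error could go either way: emapalumab could be blamed for an excess that the reporting rule created, or a real excess of non-serious infections could be dismissed as that artefact. The trial is open label, so sites know which rule applies to each patient.

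**Working it through.** The documents give no infection rate and plan no test on infections, so there is no stated figure to reproduce. The reporting rules come first, then an illustration.

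**What is required on the AE page (Protocol Sections 5.5.4.3.1 and 5.5.4.3.2)**

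| New infection | Emapalumab | Anakinra | Standard of care |
|---|---|---|---|
| Serious | required | required | required |
| Non-serious, leads to study-drug discontinuation | required | required | cannot arise: no study drug |
| Other non-serious | required | not required | not required |

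**Inputs.** n = 18 per arm (Protocol Section 7.1). Assumptions, not from the documents:

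- The true proportion p of patients with any new infection is the same in every arm, range 0.1 to 0.5.
- A share s of infected patients has a serious infection, range 0.2 to 0.8.
- Sites report exactly what is required.

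**Table of all TEAEs by system organ class and preferred term.** This table pools serious and non-serious events. The emapalumab count is binomial (18, p) and the standard-of-care count is binomial (18, ps). The expected counts are 18p and 18ps, so the expected ratio is 18p / 18ps = 1/s, whatever p is. The chance that one count exceeds the other comes from exact enumeration of the two binomials.

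| p | s | Expected, emapalumab | Expected, standard of care | Ratio 1/s | P(emapalumab higher) | P(standard of care higher) |
|---|---|---|---|---|---|---|
| 0.1 | 0.8 | 1.8 | 1.44 | 1.25 | 0.46 | 0.30 |
| 0.1 | 0.5 | 1.8 | 0.9 | 2 | 0.59 | 0.18 |
| 0.3 | 0.5 | 5.4 | 2.7 | 2 | 0.82 | 0.10 |
| 0.3 | 0.35 | 5.4 | 1.89 | 2.86 | 0.90 | 0.04 |
| 0.5 | 0.2 | 9.0 | 1.8 | 5 | 0.996 | 0.001 |

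Under one rule for all arms the expected counts are equal (for example 5.4 and 5.4 at p = 0.3). The chance that emapalumab is higher is then 0.39 to 0.43 over the same range of p, equal to the chance of the reverse. Anakinra lies between the other two arms, because infections leading to discontinuation are added to the serious ones.

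**Non-serious tabulation.** On standard of care the required count of non-serious infections is zero whatever the true rate. At p = 0.3 and s = 0.5, patients on emapalumab whose infections are all non-serious number 18 x 0.3 x 0.5 = 2.7 in expectation, against 0.

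**Neutropenia.** The AE rule is one-sided in the same way, for anakinra. Section 5.5.4.3.2 also exempts differential white cell counts from SAE reporting during screening and treatment. But Section 5.5.3.7 has differential counts drawn at Visits 1 to 7 without restriction by arm, so counts below 0.5 x 10^9/L can be derived alike for everyone. SAP Section 13.3 plans low/normal/high shift tables, which do not isolate that category.

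**Start of SAE reporting.** Section 5.5.4.3.2 starts SAE reporting at study drug initiation, which a standard-of-care patient never has. Only the letter in Appendix 3 adds randomisation to standard of care, and that letter covers only fatal and life-threatening SAEs. SAP Section 13.1 counts events from randomisation.

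**The case against.** The best defence is that restricted collection was a stated choice to spare sites during the pandemic, that the AE tables are descriptive with no test, and that the special-interest summary in SAP Section 13.1.3 is already arm-specific. All of that stands. It justifies collecting less, but not placing unequally collected events in one by-arm table without a note. The arm-specific summary leaves the Section 13.1 tables as they are.

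Three stronger readings are tempting and do not hold.

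- A reader might infer that infection risk cannot be judged at all. Serious infections are reportable in every arm regardless of causality, and SAP Section 13.1.1 tabulates serious TEAEs by system organ class and preferred term. Because prolonged hospitalisation or medical significance makes an event serious (Protocol Section 5.5.4.2.1), s could be high in these inpatients and the distortion small.
- A reader might infer that neutrophil data go unused outside the anakinra arm. SAP Sections 12.2.8 and 13.3 analyse white cell differentials in all arms; only the category below 0.5 x 10^9/L is missing.
- A reader might infer that the tables are certain to show an excess, or a significant one. With 18 per arm, ties and reversals occur: at p = 0.1 and s = 0.8 emapalumab is higher with probability only 0.46. No significance test on AEs is planned, so a p-value would say nothing about the plan's own output.

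Sites may also report more than is required, which would shrink the gap by an unknown amount.

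**Conclusion.** The concern holds for non-serious infections. Followed as written, the two documents put infections collected under different rules into the same by-arm tables, and the distortion runs against emapalumab. If true rates are equal, the expected ratio to standard of care in the pooled table is 1/s: 1.25 to 5 for s from 0.8 to 0.2. It disappears only if every infection is serious. The zero for required non-serious infections on standard of care follows from the rule alone; the ratios rest on assumed values of s and on sites reporting just what is required.

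Comparison of serious infections is sound in intent, subject to the unclear start of SAE reporting on standard of care. The primary efficacy analysis is untouched. This is a moderate defect in descriptive safety tables, cheap to remove and worth removing before they are produced.

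**What to change.** 1. Preferably, record new infections on the AE page by one rule in all three arms. Cost: a protocol change and one extra AE trigger in two arms. Otherwise, limit between-arm infection comparisons to serious infections, and show non-serious infections on emapalumab in a separate, non-comparative table with a footnote on the collection rule. Cost: SAP wording and programming only.
2. Derive severe neutropenia (below 0.5 x 10^9/L) from the differential counts at Visits 1 to 7 and tabulate it for all three arms, in addition to the shift tables in SAP Section 13.3. Cost: programming; no new data.
3. Do not present AEs leading to study-drug discontinuation or infusion reactions as comparisons with standard of care. That arm has no study drug, so its zero carries no information. Cost: a footnote or a change of table layout.
4. State in Protocol Section 5.5.4.3.2 that SAE reporting on standard of care starts at randomisation, as the Appendix 3 letter does. Reconcile the emapalumab events of special interest in SAP Section 13.1.3 with the wider definition, covering every new infection, in Protocol Sections 4.2.1 and 5.5.4.3.1 and SAP Section 3.4.3. Cost: text only.
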